4.4. Sample size calculation

A meta-analyses of recent smartphone-based physical activity interventions found a small to medium average effect size (standardized mean difference) of 0.31 on daily minutes of physical activity [55]. The effect sizes in individual studies ranged between -0.29 to 0.70. We expect the main treatment effect in our study (T2 v C) to be towards the higher end of this range. Our second treatment effect (T2 versus T1) is expected to be somewhat smaller. Given this, we aim to recruit 600 participants to the trial, randomized in a 1:1:1 allocation ratio to the three arms (200:200:200 participants). The average attrition rate in previous web-based physical activity interventions was 20% [56]. However, as we incentivize participation throughout the duration of our study using both psychological and tangible rewards, we estimate that attrition will be 15% in our study. This would leave us with a final total sample size of 510, once attrition is accounted for. Taking into account the potential maximum deviation from a 1:1:1 allocation ratio which may arise due to the stratified block randomization procedure, our intended sample size (n=600) will give us power to detect effect sizes greater than or equal to the average effect found in the metaanalysis (0.31), which should be adequate to detect our main treatment effect of T2 versus C.

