7.1. Primary outcome

Outcome measures are collected at baseline, immediately post-intervention, 3 months follow-up, and 12 months follow-up (see appendix F1 for schematic overview of data collection during the trial). Physical activity will additionally be assessed at the intervention midpoint. The primary outcome of this research project is objectively measured MVPA, as measured by the Fitbit.

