7.4. Confounders

To adjust data-analyses for potential confounders, information on type of blood pressure condition, age, lactation status, household composition, education, trait self-control, and habit is self-reported in-app at baseline.

8. Interim analysis and stopping rules

We anticipate no safety issues with this study. As such, no interim analysis is planned, and no stopping rules are defined.

C1. Research Protocol i2be Version 2 dd 29-03-2021

9. Randomization

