9.3. Implementation

Following email invitation from health care professionals (in case of hospital recruitment) or the research team (in case of recruitment through patient organizations), interested participants click on a link in the email that will lead them to an eligibility questionnaire hosted on the researcher platform of Avegen (digital health company responsible for developing and hosting the researcher platform and participant app). Once eligibility has been established, the participant will be asked for informed consent. Following informed consent, participants will be asked their name, email address, and postal address to send the Fitbit and a soft measuring tape. Next, participants will receive an email from Avegen to download the i2be and Fitbit apps from the Google Play Store (for Android phones) or App Store (for iPhones), a pdf of the Welcome Pack, and a message that the Fitbit will be sent in the post mail. The Welcome Pack consists of instructions on the configuration of the Fitbit app and the i2be app, an explanation of the Fitbit device, and an explanation on the i2be points and reward system.

When using the i2be app for the first time, participants will be asked to choose their preferred language (Dutch or English) and register with their email address. Subsequently, participants will be stratified on two factors (i.e. on time since pregnancy [< 12 months post-partum versus ≥ 12 months post-partum] and self-reported baseline MVPA [low, medium, high]), and randomly allocated (1:1:1) in-app to one of the three intervention arms, i.e. the control group (C), treatment 1 (T1), or treatment 2 (T2). The

participants will be shown a 2 minute video that introduces i2be. The 8 week intervention period will then start.

10. Statistical analysis

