10.1. Primary analysis

The primary analysis will be a modified intention-to-treat analysis, the deviation from a full intention-to-treat analysis being that we exclude participants with missing dependent variable data (available case analysis). Linear regression will be used to assess differences between groups. The main test of i2be is the test T2 versus C in order to gain insight into the effectiveness of targeting the three types of processes hypothesized to impact MVPA. Second, we aim to test differences between T2 and T1 to gain insight into the contribution of volitional and automatic processes over motivational processes only in bridging the intention behavior gap. Third, we will test the difference between T1 and C to gain insight into the differential effectiveness of targeting motivational processes compared to treatment as usual. Variation in MOA variables will be investigated to gain insight into the mechanisms underlying the effects of BCTs. Sensitivity analyses will be carried out to assess the robustness of results to the missing data strategy adopted.

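### The protocol's only adjustment list omits both randomisation strata and baseline Fitbit MVPA, and the primary regression names none of them

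*Protocol*

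**What the plan says.** All references are to the protocol.

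- **Primary model, section 10.1.** "Linear regression will be used to assess differences between groups". No covariates are named, and the model is not described as unadjusted.
- **Adjustment variables, section 7.4.** The purpose is given as "To adjust data-analyses for potential confounders", and the list reads: "information on type of blood pressure condition, age, lactation status, household composition, education, trait self-control, and habit is self-reported in-app at baseline".
- **Randomisation, section 9.3.** "participants will be stratified on two factors (i.e. on time since pregnancy", in two classes split at 12 months post-partum, and on "self-reported baseline MVPA [low, medium, high]), and randomly allocated (1:1:1) in-app". Section 4.4 confirms the method when it allows for departures from 1:1:1 "which may arise due to the stratified block randomization procedure".
- **Outcome, section 7.1.** "The primary outcome of this research project is objectively measured MVPA, as measured by the Fitbit". The same section schedules outcome measurement at baseline as well as at follow-up.

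Time since pregnancy, self-reported MVPA category and baseline Fitbit MVPA do not appear in 7.4 or 10.1, and no other section places them in an analysis model.

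**The concern.** The design treats time since pregnancy and prior activity as important enough to stratify on, and it schedules a baseline measurement of the primary outcome. The analysis text uses none of this.

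Two losses follow if the text is applied as it stands. First, stratified randomisation balances the arms on the strata, which reduces the true variance of the treatment difference. A model without the strata does not credit that reduction, so its standard errors are too large, its intervals too wide and its tests conservative. Second, a baseline value of the outcome usually predicts the later value, and leaving it out leaves that variation in the residual.

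The sample size gives little slack to absorb this. Section 4.4 also expects the T2 versus T1 effect to be somewhat smaller than T2 versus C, so lost precision would matter at least as much there.

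**Working it through.** **Inputs from section 4.4:** 600 randomised 1:1:1, 15% attrition, standardised mean difference (SMD) 0.31. **Assumed, because the protocol gives no figure:** two-sided 5%, 80% power as the benchmark, the correlation ρ between baseline and follow-up Fitbit MVPA, and the share R² of outcome variance explained by the strata.

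**1. The plan's own figure.** 600 × (1 − 0.15) = 510, or 170 per arm, as stated. The standard error of the difference in SD units is √(2/170) = 0.1085.

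- Power for 0.31: Φ(0.31/0.1085 − 1.960) = Φ(0.898) = 81.5% (81.3% with the exact t distribution).
- SMD detectable at 80% power: (1.960 + 0.842) × 0.1085 = 0.304.
- Evaluable number needed for 0.31 at 80% power: 2 × (1.960 + 0.842)²/0.31², rounded up to 164 per arm.

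So 0.31 is reached without adjustment, with 6 participants per arm to spare.

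**2. Adding baseline MVPA.** The residual SD is multiplied by √(1 − ρ²). Power is Φ(0.31/(0.1085 × √(1 − ρ²)) − 1.960), and the other quantities scale in the same way.

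| ρ (assumed) | SD factor | Power, SMD 0.31 | SMD detectable at 80% | n per arm for 0.31 at 80% | 95% CI half-width (SD) |
|---|---|---|---|---|---|
| 0 (unadjusted) | 1.000 | 81.5% | 0.304 | 164 | 0.213 |
| 0.3 | 0.954 | 85.0% | 0.290 | 149 | 0.203 |
| 0.5 | 0.866 | 91.0% | 0.263 | 123 | 0.184 |
| 0.7 | 0.714 | 97.9% | 0.217 | 84 | 0.152 |

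As an illustration for a smaller contrast, an SMD of 0.20 has 45.4% power unadjusted and 48.9%, 56.7% and 73.3% at ρ = 0.3, 0.5 and 0.7. The value 0.20 is chosen here; the protocol gives no figure for T2 versus T1.

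**3. Adding the strata alone.** If the strata are balanced by design but left out of the model, the true type I error is 2 × (1 − Φ(1.960/√(1 − R²))) and power is Φ(0.898/√(1 − R²)). With the strata in the model, power is Φ(0.31/(0.1085 × √(1 − R²)) − 1.960).

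| R² (assumed) | Type I error, strata ignored | Power, strata ignored | Power, strata included |
|---|---|---|---|
| 0.05 | 4.4% | 82.2% | 83.5% |
| 0.10 | 3.9% | 82.8% | 85.4% |
| 0.20 | 2.8% | 84.2% | 89.2% |
| 0.30 | 1.9% | 85.9% | 92.7% |

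The gains in steps 2 and 3 overlap, because self-reported and device-measured activity at baseline should be related. They must not be added together.

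**The case against.** The strongest reply is that 10.1 is silent, not wrong. A linear regression is fully compatible with the covariates proposed here, and a covariate set is commonly left to a statistical analysis plan, which may exist. Section 7.4 sits among the outcomes, describes self-reported data collection, speaks of data analyses in general, and does not claim to be complete. Baseline Fitbit MVPA is device-measured and the strata are captured at randomisation, so there may have been no reason to list them there.

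Much of this stands. A reader might infer that the plan specifies an unadjusted primary analysis, or excludes these variables. It does neither. What remains is that the protocol does give an adjustment list, and that the only list it gives lacks the variables with the strongest claim from the design.

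Other stronger readings also fail:

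- **That the trial is underpowered or its error rate inflated.** The detectable effect in 4.4 holds at about 81% power without adjustment, and ignoring the strata lowers the type I error.
- **That omitting baseline MVPA discards most of the explainable variance.** The protocol gives no correlation. At ρ = 0.3 the baseline explains 9% of outcome variance (0.3²), and at 0.7 it explains 49%.
- **That calling the 7.4 variables confounders, or including habit, is an error.** The list serves analyses in general, including those of mechanism variables, where randomisation does not remove confounding. Habit is measured at baseline and is a legitimate covariate.

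Two cautions apply to the size of the gain. The comparator is a wholly unadjusted model; adjusting for the 7.4 variables might recover part of the loss. Section 9.3 describes no Fitbit run-in before allocation, so it is unclear whether a clean pre-randomisation device value will exist.

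**Conclusion.** The point holds as a weakness in the stated adjustment set, not as a declared decision against adjustment and not as a threat to validity. Sections 7.4 and 10.1, read together, lead to a model without the strata or the baseline outcome. Such a model would be conservative to the extent that the strata predict the outcome, and would give up precision that the design makes available.

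Under assumed correlations of 0.3 to 0.7, the loss is the difference between about 81% power and 85% to 98% for an SMD of 0.31, or between a detectable SMD of about 0.30 and one of 0.29 to 0.22. These figures rest on 170 analysed per arm, a two-sided 5% test, an unadjusted comparator, and a baseline measured before allocation. The direction is well supported; the size depends on a correlation that the protocol does not supply.

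**What to change.** State in section 10.1 that the primary linear regression of follow-up Fitbit MVPA includes:

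- trial arm;
- time since pregnancy (below 12 months versus 12 months or more);
- self-reported baseline MVPA category (low, medium, high);
- baseline Fitbit MVPA as a continuous variable, provided that it is measured before allocation.

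If the device baseline is recorded only after allocation, leave it out and adjust for the two strata alone, which are recorded before allocation. The protocol should say which case applies. The 7.4 variables can stay as additional covariates or be used in a sensitivity model, with the choice fixed in advance.

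For the strata the cost is one sentence, with no new data and no added participants. The same holds for the device baseline if it already precedes allocation. If it does not, obtaining one would be a change of procedure, and the fix proposed here does not depend on it.

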10.2. Subgroup analyses

To assess whether the e-health intervention has differential effects across educational level, subgroup analysis by educational level will be performed.

10.3. Additional analyses

A test of the IBC model will be conducted using structural equation modelling on the relationships between MOA variables as hypothesized by the model. Process evaluation of the intervention will entail fidelity measures (i.e. measures of participants' interaction with the app), as well as qualitative research among participants on their experiences with and feelings regarding the app.

11. Safety considerations

Given the nature of the intervention participant safety issues are not anticipated in this study. As such no recording of adverse events will be undertaken as part of the study.

12. Ethical considerations

Staff at the research site will adhere most strictly to all applicable legal, ethical, and safety provisions of the Netherlands and the EU. The study will be conducted in accordance with the principles of the Declaration of Helsinki [61]. No minors and/or incapacitated adults will participate in this study. To obtain dispensation from the statuary obligation to provide insurance, because participating in the study is without risks, we will submit a reasoned request to the accredited METC.

13. Administrative aspects, monitoring and publication

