objectively measured (resting heart rate) and self-reported physiology measurements (body mass index, waist-hip-ratio, cardiorespiratory fitness), as well as subjective well-being. Tertiary outcomes include self-reported mechanism of action variables in order to assess the mechanisms underlying the effects of BCTs. Objectively measured outcomes will be captured by Fitbit activity trackers (Fitbit Inspire 2), and all other outcomes measures will be self-reported into the i2be app. Outcome measures will be assessed at baseline, immediately post-intervention, at 3 months follow-up, and at 12 months follow-up. Physical activity will additionally be assessed at the intervention midpoint. Effectiveness will be determined by a modified intention-to-treat analysis. Additionally, a process evaluation will be performed immediately post-intervention.

Nature and extent of the burden and risks associated with participation, benefit and group relatedness: Not applicable.

1. Introduction and rationale

The reduction of cardiovascular disease (CVD) is a public health priority, as CVDs are among the leading causes of poor health worldwide [1]. Insufficient physical activity, poor dietary habits, tobacco, and alcohol use are some of the most important behavioral risk factors for CVD [1]. Cardio metabolic risk factors for CVD such as hypertension, overweight and obesity often go hand in hand with behavioral risk factors for CVD [2, 3]. Some cardio metabolic risk factors for CVD are specific to women, including hypertensive pregnancy disorders [4, 5]. For example, preeclampsia is a hypertensive pregnancy disorder complicating two to eight percent of pregnancies worldwide, leading to acute clinical consequences of maternal and neonatal morbidity and mortality, and a two to seven fold risk for CVD later in life in comparison to women with a normotensive pregnancy [6, 7].

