4.3. Exclusion criteria

A person who meets any of the following criteria will not be eligible for participation in this study:

C1. Research Protocol i2be Version 2 dd 29-03-2021

- <18 years of age
- Pregnant at time of inclusion
- <3 months post-partum
- Any physical health limitations preventing physical activity (e.g. illness, injury, surgery, rehabilitation)
- No working knowledge of Dutch or English language
- No possession of a smartphone

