7.2. Secondary outcomes

Secondary outcomes consist of physiological and well-being measures. Resting heart rate will be measured by the Fitbit. Other physiological measures are taken at home and self-reported in i2be by participants, including body mass index, waist-to-hip ratio, and cardiorespiratory fitness. Text instructions on the correct performance of home measurements will be provided to participants in-app. A soft measuring tape will be sent to participants along with the Fitbit. Subjective well-being is self-reported in-app.

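### The protocol rules out recording adverse events and states no tracking of pregnancy, injury or illness after entry, so harm by arm cannot be reported and the effect of such events on outcomes cannot be checked

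*Protocol*

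**What the plan says.** Section 11 gives its reason first, "Given the nature of the intervention participant safety issues are not anticipated in this study", and then the rule: "As such no recording of adverse events will be undertaken as part of the study". Section 8 likewise expects no safety issues and sets no interim analysis or stopping rules.

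Section 4.3 bars women on these grounds, among others:
- "Pregnant at time of inclusion"
- "<3 months post-partum"
- "Any physical health limitations preventing physical activity (e.g. illness, injury, surgery, rehabilitation"

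Section 7.4 lists the potential confounders. Lactation status is among them; pregnancy, illness and injury are not. The list ends "trait self-control, and habit is self-reported in-app at baseline".

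Section 7.1 sets outcome measurement at baseline, post-intervention, 3 months and 12 months, with an extra midpoint measurement of physical activity. Section 7.2 names resting heart rate from the tracker and self-reported physiology, "including body mass index, waist-to-hip ratio, and cardiorespiratory fitness". Sections 5.1.4 and 5.1.5 leave the home measurements and questionnaires to Appendix F1, which is not in the text at hand.

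**The concern.** The protocol treats pregnancy, recent birth and physical limitation as important enough to bar entry, and then states no way of knowing whether they arise later. They are foreseeable. Section 3 describes the app as showing women of 20 to 50 years to match the population, and Section 5.1.2 counts the last two follow-ups from the end of the 8-week intervention.

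Two things are at stake.

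1. **Harm by arm.** All arms are advised to be active, and Treatment 2 adds weekly activity goals to which participants can commit points (Section 5.2.2). Activity-related injury is the obvious harm to compare, and Section 11 excludes recording it. A later analysis plan cannot recover events that were not collected.
2. **Interpretation of outcomes.** A pregnancy, injury or illness can move every outcome named above, including the primary one. Women may leave without giving a reason (Section 4.5), no data follow drop-out (Section 6.1), and the analysis uses available cases (Section 10.1). If such events drive drop-out differently by arm, the planned missing-data sensitivity analyses have no stated event data to draw on.

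**Working it through.** **The plan's own figure.** Section 4.4 randomises 600 women 1:1:1 and expects 15% attrition: 600 × 0.85 = 510, or 170 per arm. This agrees with the protocol. Section 4.4 states neither a significance level nor a target power, so a two-sided 5% level is assumed. For a standardised difference of 0.31:

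power = Φ(0.31 / √(2/170) − 1.96) = Φ(2.858 − 1.96) = 81.5%.

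The 0.31 comes from a meta-analysis of physical activity. It serves here only as a yardstick for the other outcomes.

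**Effect of unrecorded events (assumed inputs).** The protocol gives no event rates and no SDs. Suppose a share p of every arm has an event that shifts the outcome by k SD. Then:

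- expected difference between arms due to the events: zero
- SD becomes √(1 + p(1 − p)k²)
- if affected women also gain nothing from treatment, the effect becomes 0.31 × (1 − p)

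| p | k | SD factor | Power, noise only | Power, noise and dilution |
|---|---|---|---|---|
| 3% | 0.5 | 1.004 | 81.3% | 78.9% |
| 5% | 1.0 | 1.023 | 79.7% | 75.6% |
| 10% | 1.0 | 1.044 | 78.2% | 69.3% |
| 15% | 1.5 | 1.134 | 71.2% | 57.2% |

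**When bias arises.** It needs event rates that differ because of the arm. A 5-point difference gives 0.05 × k, that is 0.025 SD at k = 0.5 and 0.075 SD at k = 1.5. Against 0.31 this is 8% to 24% of the effect (0.025/0.31 and 0.075/0.31). Chance differences in rate have standard error √(2p(1 − p)/170), which is 2.4 points at p = 5% and 3.9 points at p = 15%. These are ordinary sampling error, already contained in the larger SD, and must not be counted a second time.

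**Sensitivity to the assumed SD.** On the scale of body mass index, variance inflation is 1 + p(1 − p) × shift²/SD². Take an assumed pregnancy shift of 3 kg/m² and p = 5%, 10% and 15%:

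- SD 1.5 (a change score): 1.19, 1.36, 1.51
- SD 5 (a cross-sectional value): 1 + 0.0475 × 9/25 = 1.02; 1 + 0.09 × 9/25 = 1.03; 1 + 0.1275 × 9/25 = 1.05

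For resting heart rate, with an assumed shift of 10 bpm and SD of 8, the factors are 1.07, 1.14 and 1.20. Section 10.1 specifies linear regression and no change-score analysis, so the large values for body mass index cannot be taken as the expected case.

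**The case against.** Several stronger readings are tempting, and the protocol does not support them.

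- **A reader might infer that these events are never recorded.** Appendix F1 is not shown and could hold a follow-up item. Section 7.4 says what is asked at baseline, not that it is asked only then. Pregnancy is not normally an adverse event, so Section 11 does not itself forbid asking about it. What can be said is that the body text states no tracking. Appendix F1 does not rescue the adverse-event limb, because Section 11 excludes that recording outright.
- **A reader might infer that the secondary outcomes are biased.** The arms are randomised, so events unrelated to arm add noise and dilute the effect without expected bias. This objection stands.
- **A reader might see a contradiction between the background risk in Section 1, "a two to seven fold risk for CVD later in life", and Section 12, which treats participation as free of risk.** The first is long-term disease risk compared with women after a normotensive pregnancy. The second concerns taking part in the trial. They do not conflict.
- **The analysis of such events can be left to the statistical analysis plan.** This is fair for the method. It is not fair for data collection, which the protocol fixes.
- **Activity is only advised, and women with physical limitations are excluded.** That lowers the expected harm, but gives no means of showing that harm was low or similar across arms. The process evaluation does not fill the gap: the Summary places it immediately post-intervention, and Section 10.3 aims it at use and experience of the app.
- **Setting body measures to missing during pregnancy would be worse.** Under available-case analysis it removes women on a post-randomisation event and could introduce selection. This is right as regards the main analysis.

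**Conclusion.** The point holds in a limited form and should be acted on. Section 11 is an explicit decision, not an omission, and under it activity-related harm cannot be reported systematically by arm. Separately, the body text states no tracking of pregnancy, injury or illness after entry, so their effect on the outcomes and on drop-out cannot be examined unless Appendix F1 provides for it.

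The statistical cost is uncertain and may be small. It runs from almost nothing to a substantial loss of power, depending on assumed event rates, shifts and SDs that the protocol does not supply. No bias is expected unless events, or the drop-out they cause, differ by arm. The planned sample size is unaffected.

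**What to change.** Replace the Section 11 sentence on adverse events. State that at the existing measurement points (midpoint, post-intervention, 3 months and 12 months) the app asks whether the participant is, or has been, pregnant since the last contact, and whether an injury, illness or cardiovascular event has limited her activity. If Appendix F1 already contains such items, cite them. Report the answers by arm.

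Keep all participants in the main analyses, subject to the available-case rule already in Section 10.1. Add a pre-stated sensitivity analysis of body mass index, waist-hip ratio, fitness and resting heart rate that excludes or accounts for values taken during pregnancy.

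The cost is a few in-app items, an ethics notification, one table and slightly more burden for participants. One limit remains: the items reach only women who are still responding, so drop-out related to these events becomes partly, not fully, checkable.
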